## **7 UNBLINDING**

The PI and site staff are blinded to subject treatment throughout the study and do not have access to the randomization code. Unblinding assignments will be maintained by the unblinded statistician at Emmes that prepared the randomization code.

[figure not shown]
In case of an unexpected and related SAE for which knowledge of the subject's treatment is required for the subject's clinical care and safety, the blind for that subject may be broken. The PI must contact the Medical Monitor with an explanation of the need to obtain the study treatment information. The Medical Monitor will confer with the Sponsor prior to the authorization of the blind to be broken. Complete documentation of breaking the blind must be recorded in the subject's source documents including the date and time the blind was broken, the reason for the decision to unblind, and the names of the personnel involved in the decision. The unblinded statistician will conduct the unblinding, notify the site PI, and also the DSMB of all such cases.

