## **11.5 Unexpected Event**

An AE is considered unexpected from a regulatory perspective when it is not listed in the package insert/prescribing information, Investigator's Brochure (IB), or, if none of these is available, the general investigational plan (e.g., study protocol, informed consent) for the study product at the specificity and severity that has been observed. Unexpected is a regulatory term, whereas unanticipated is more clinical and should not be used interchangeably. For example, some AEs can be anticipated to occur as a result of a disease or in an older population (e.g., cancer-related deaths in a cancer trial, strokes or acute myocardial infarctions in an older population). However, for reporting purposes, these

anticipated events are not “expected” because they are not listed in the IB (i.e., the study product is not suspected or known to cause them). The Sponsor or designee is responsible for determining expectedness.

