#### **11.8.3.4 Pregnancy**

Pregnancy is not considered an AE, but any pregnancies that occur during the study will be tracked on a pregnancy case report form. Pregnancy is an exclusion criterion. If a study subject was pregnant on the day of study product administration (e.g., due to a false negative pregnancy test) or becomes pregnant afterwards, the subject will be followed through the end of her pregnancy. The subject will not receive any additional doses of

study medication but would be encouraged to continue to attend the remaining study visits. If the subject is unwilling to do so, she should be asked to return to the study center to complete the assessments specified in the End-of-Study Visit (Week 52). Any complications of pregnancy or termination of pregnancy due to medical reasons will be considered a SAE as defined in Section 11.1. The PI should be informed immediately of any pregnancy, and all available pregnancy information should be entered into Advantage eClinical within 24 hours of becoming aware of the event. The PI should counsel the subject and discuss the risks of continuing with the pregnancy and the possible effects on the fetus. The site will be asked to follow-up with the subject periodically during the pregnancy for ongoing health and safety information through the conclusion of the pregnancy. Follow-up information detailing the outcome of the pregnancy should be entered into the Advantage eClinical system as it becomes available. If the pregnancy results in normal childbirth with a healthy, normal infant, no SAE will need to be reported. If the pregnancy results in a congenital anomaly/birth defect, an SAE must be reported following the SAE reporting procedures in the protocol. Any premature termination of the pregnancy will be reported.

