#### **13.3.2 Safety Analysis**

All randomized subjects who received treatment will be included in a final safety data analysis which will include all data through Week 52 as the as-treated cohorts. In addition to descriptive summaries of all AEs by treatment group, Fisher's Exact test will be used to compare the incidence of the most frequent AEs or SAEs between treatment groups. The MedDRA system will be used to map each AE verbatim term to the system organ class (SOC) and preferred term (PT) for summary purposes. AE data, including the AE verbatim term and the associated AE preferred term, will be provided in the subject data listings. Note that once enrollment of TOL-3021 studies is expanded to adolescent participants aged 12.0 to <18 years of age, data from adolescent participants will be summarized and presented separately from data on adult participants in all subsequent DSMB review meetings.

Adverse event incidence summaries, including incidence rates of SAEs and TEAEs, will be generated on a monthly basis on live data. These will be reviewed in real time by the Sponsor and Emmes, with the treatment groups labeled as "A" and "B." An excessive rate in any specific AE or SAE may result in referral to the DSMB for review. The study statistician will maintain these reports and all resulting correspondence. The code may be requested to be broken by the DSMB after receiving Sponsor approval.

Other safety data, such as laboratory data, physical examination data, and abnormal findings, will be tabulated and/or graphically displayed. Concomitant medications used during the study will be summarized. Medications discontinued prior to the randomization date will be excluded from the summary.

Safety data collected after Week 52 will be analyzed separately from safety data collected during the controlled trial period.

After 6 subjects aged 14-<18 years of age have been enrolled with the last subject having a minimum of 2 injections with at least 1 week follow-up after the 2nd injection. Safety data from these initial subjects will be evaluated before opening the study to subjects 12 and older.

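### The only stated route for breaking a subject's blind depends on how the event is classified, not on whether the subject's care needs the allocation, and a DSMB request for the code is subject to sponsor approval

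*Protocol*

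**What the plan says.** On the individual blind, Section 7 sets the condition: "In case of an unexpected and related SAE for which knowledge of the subject's treatment is required". The need must arise from that person's own care or safety. The steps that follow are:

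- The investigator explains to the Medical Monitor why the allocation is needed.
- "The Medical Monitor will confer with the Sponsor prior to the authorization of the blind to be broken".
- The unblinded statistician at the CRO then breaks the blind and notifies the site investigator and the DSMB.

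On site access, the same section says: "The PI and site staff are blinded to subject treatment throughout the study and do not have access to the randomization code". It gives no other route, no time limit and no out-of-hours arrangement.

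Three other sections bear on who meets the condition:

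- Section 11.5: "The Sponsor or designee is responsible for determining expectedness".
- Section 11.8.2 asks for evidence that suggests causality. Being unable to rule out a relationship is not enough, and neither is timing alone.
- Section 11.8.3.4 says that pregnancy is not an adverse event, yet "The PI should counsel the subject and discuss the risks of continuing with the pregnancy and the possible effects on the fetus".

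On the DSMB, Section 13.3.2 describes monthly adverse event summaries with arms labelled A and B, reviewed by the sponsor and the CRO, and possible referral of an excessive rate to the DSMB. It then says: "The code may be requested to be broken by the DSMB after receiving Sponsor approval". Section 5.4 adds that the sponsor's view prevails if it and the DSMB cannot agree.

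**The concern.** A code break for an individual serves that person's care, so the natural test is whether the treating physician needs the allocation. Section 7 contains that test but adds two regulatory classifications, unexpected and related. These exist to decide how an event is reported to authorities, and neither says whether the allocation matters for treatment. The sponsor makes one of the two determinations and must also be consulted before the break is authorised.

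At stake for a subject is that a physician with a real need has no written route, or has to wait. At stake for oversight is that the DSMB, when it wants to know which arm carries an excess of events, must first get the agreement of the party whose trial it monitors.

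**Working it through.** No arithmetic applies: the plan states no figure on this point, and the question is what the procedure allows. The check is to run types of event through Section 7 as written, assuming in each case that the allocation is needed for care.

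| Event | Unexpected? | Related? | SAE? | Within the stated route? |
|---|---|---|---|---|
| Unexpected SAE, positive evidence of causality | Yes (sponsor decides, 11.5) | Yes | Yes | Yes, after the sponsor is consulted |
| SAE of a kind and severity already listed, positive evidence of causality | No | Yes | Yes | No |
| Unlisted SAE of unclear cause | Yes | No (11.8.2 needs evidence) | Yes | No |
| Non-serious event | Either | Either | No | No |
| Pregnancy without complication | Not applicable | Not applicable | No (11.8.3.4: not an adverse event) | No |

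Clinical need is the same in all five rows by construction, yet only the first row qualifies. The added classifications, not the need, separate the rows.

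The steps for the qualifying row are:

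1. The investigator judges causality (11.8.2).
2. The sponsor or its designee determines expectedness (11.5).
3. The investigator explains the need to the Medical Monitor (Section 7).
4. The Medical Monitor confers with the sponsor (Section 7).
5. The unblinded statistician breaks the blind (Section 7).

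The sponsor or its designee thus enters twice, at steps 2 and 4, before release. No step has a time limit.

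For the DSMB, four statements need to be read together:

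- 13.3.2: a request to break the code follows sponsor approval.
- 5.4: the sponsor's view prevails in an unresolved disagreement.
- Synopsis, data handling and blinding: unblinded results of the Week 24 interim go to the DSMB.
- 13.2: the DSMB reviews that interim in a blinded manner.

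The last two conflict. Even if the synopsis is the one that applies, it covers a single planned look after the first 30 subjects reach Week 24. It gives the DSMB no access of its own when a signal arises at another time. No other section supplies a route that avoids the sponsor.

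**The case against.** The strongest case against is that Section 7 is permissive. It does not contain the word only, and it has the Medical Monitor confer with the sponsor, not obtain consent. A reader might infer that the sponsor can veto an individual code break, or that events outside the condition cannot be unblinded. The documents support neither reading: conferring is a mandatory prior consultation, and silence about other events is not a prohibition. What stands is that this is the sole route described and that sites hold no code, so other events have no written procedure.

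Protective action also does not depend on the code. Section 5.3.1 lets the investigator discontinue study drug whenever medically necessary, and 11.8.3.4 ends dosing in pregnancy whatever the arm. That is right and limits the consequence. It does not help where the allocation itself bears on treatment or counselling.

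A severe hypersensitivity reaction is a tempting example, because such reactions are events of special interest. It falls outside the route only if it is listed as expected or judged not related. Expectedness rests on the Investigator's Brochure, which is not available here, and being of special interest does not make an event expected.

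On the DSMB, the approval sentence stands within the A/B adverse event review, and extending it to every review under the stopping rules in 5.3.2 would be an inference. With 2:1 allocation (66 and 33 of 99), group sizes could also reveal which label is active, if the tables show denominators. The protocol does not say that they do, and group sizes would not give an individual's allocation. The DSMB charter may say more, but it could not be seen, and the protocol's own sentence requires approval.

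**Conclusion.** The point holds as a defect of wording with a safety and oversight consequence. As written, an event in which the allocation is needed for care can fall outside the only stated route or be delayed by a required consultation. The DSMB's access to the code in the A/B review depends on sponsor approval; that dependence is explicit, whereas for individual subjects the text requires consultation only.

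The size cannot be quantified, and two figures that a reader might use do not show harm. In the phase 2a study, 7 of 80 subjects had SAEs (2 + 1 + 4), all considered unrelated, so none would have met the condition; but nothing suggests that any of them needed the code. Likewise, with 52 weekly doses and site dosing at randomisation and Weeks 1, 2 and 4, 52 − 4 = 48 doses are given at home (47 for the first six adolescents, who are also dosed on site at Week 3). That says where doses are given, not that a code break would be needed or slow.

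The conclusion assumes that sites follow Section 7 literally and that no document outside the protocol provides another route.

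**What to change.** **Section 7.** Replace the unexpected-and-related-SAE condition with any event, including pregnancy, for which the investigator judges that knowledge of the allocation is needed for the subject's care. Have the code released to the investigator on request, by the unblinded statistician or an equivalent code-break route. Tell the Medical Monitor and sponsor afterwards that a break occurred, but not the allocation, so that the sponsor's blind to Week 24 is kept. Retain the existing documentation and the notice to the DSMB.

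The protocol does not show that the randomisation system could release the code itself. Section 6 says that it assigns vials, while Section 7 places the unblinding assignments with the statistician. The release route and its availability therefore need to be settled.

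**Section 13.3.2.** Replace the sponsor-approval clause with a direct request from the DSMB to the unblinded statistician. Reconcile this with the clause in 5.4 under which the sponsor's view prevails, and settle whether the DSMB sees unblinded interim data, on which the synopsis and 13.2 disagree. The DSMB charter should match.

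**Cost.** An amendment of a few sentences, a working release arrangement, and probably a few more individual unblindings, each documented as already required. No analysis or sample size changes.

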## **8 MATERIALS**

### **8.1 Study Drug**

TOL-3021 is a 3.3 Kb bacterial plasmid expression vector containing the coding sequences for the human proinsulin (hINS) gene. Important functional and control features of TOL-3021 include the human cytomegalovirus (CMV) immediate-early gene promoter/enhancer, the bovine growth hormone gene polyadenylation signal, the kanamycin resistance gene, and the pUC origin of replication for propagation of the vector in *E. coli*. The backbone of TOL-3021 has been modified to decrease the number of immunostimulatory CpG sequences and substitute immunosuppressive sequences (Figure 4).

**Figure 4. Structural Diagram of TOL-3021**

TOL-3021 is formulated in a phosphate-buffered, calcium-containing sterile solution for IM injection. The nominal concentration of TOL-3021 in this solution is 2 mg DNA/mL. TOL-3021 is provided in a sterile single-use 2 mL vial. Placebo is a phosphate-buffered sterile saline solution packaged in a sterile single-use 2 mL vial.

**8.2 Storage, Dispensing, and Reconciliation of Study Drug**

**8.2.1 Receipt and Storage of Study Drug**

Study drug will be supplied in individual cartons containing single-use vials. The carton and the vial are labelled with a barcode that can be scanned for maintaining inventory and dispensing records. The site will maintain shipping documents and acknowledge receipt of study drug to Emmes. Study drug will be shipped frozen and must be placed in a locked freezer in a secured location and maintained at  $-20 \pm 5^{\circ}\text{C}$  upon receipt until dispensing for subject treatment.

**8.2.2 Dispensing of Study Drug**

Study drug (active or placebo) will be labelled with required information on the vials of study drug while maintaining the study blind. Study drug will be designated by the randomization scheme for treatment of a specific subject throughout the study. Study drug will be tracked via a scannable barcode label affixed to the box containing the vial of study drug and reported in Advantage eClinical when study drug reaches the site. In addition, a tear-off label on the study drug carton will be removed and placed in the subject’s source documents. An individual vial of study drug will be dispensed to the appropriate site staff

for administration to a subject at randomization, Week 1, Week 2, and Week 4 clinic visits. The study drug vial for Week 3 administration at home will be dispensed at the Week 2 visit, except for the first 6 subjects aged 14-<18 in Cohort B. These subjects will have a visit at Week 3 and will receive their study drug injection at the visit. When a subject will self-administer study drug following a clinic visit, the appropriate number of study drug vials will be dispensed for at-home use until the next clinic visit. Vials dispensed to subjects will be stored under refrigeration until use. Subjects will be given instruction on storage and administration of study drug. The PI (or designee) is responsible for maintaining inventory records, acknowledging receipt of study kits, and dispensing records that track distribution of medication to subjects. Subjects will be instructed to return used vials and any unused vials at each study visit and PIs (or designees) are responsible for recording receipt of returned used vials/unused vials for accountability.

### **8.2.3 Study Drug Accountability**

- Drug accountability forms will be provided by Emmes to track receipt, dispensing and return of all study drug vials. Accountability forms will contain the following information:
- ID number of vials received, including date and identifying information provided on label
- ID number of vials currently stored in freezer at  $-20 \pm 5$  °C storage
- ID number of vials dispensed by date to each subject, identified by a unique subject ID number
- Non-administered disposition (e.g., wasted, broken)
- ID number of vials returned to site staff for subsequent accountability and disposal, if applicable
- ID number of vials destroyed on site

These records will be made available to the study Clinical Research Associate (CRA) for review during monitoring visits.

Emmes will provide forms in Advantage eClinical to facilitate investigational product inventory control. All investigational product accountability forms and treatment logs must be retained in the PI's permanent study file. These records must be available for inspection by the Sponsor, its designees, or regulatory agencies at any time after study completion.

The PI (or designee) must maintain 100% accountability for all investigational products received and dispensed during his or her entire participation in the study. Proper drug accountability includes, but is not limited to:

- Frequently verifying that actual inventory matches documented inventory;
- Verifying that all containers used/broken/unused/lost are documented accurately on the log;
- Verifying that required fields are completed accurately and legibly.

If any dispensing errors or discrepancies are discovered, the Sponsor and Emmes must be notified immediately.

At study closeout, the PI (or designee) or pharmacy will be required to reconcile all received, dispensed, and returned drug supplies.

#### **8.2.4 Returns and Destruction of Study Drug**

The site will receive instruction from the Sponsor regarding the final disposition of any remaining investigational products. The used vials must be kept separately for accountability. At completion of the study (i.e., after the Week 52 visit of the last subject), there will be a final reconciliation of investigational products shipped, investigational products consumed, and investigational products remaining. Any discrepancies noted will be investigated, resolved, and documented prior to return or destruction of unused investigational products. All unused vials will be returned to the Sponsor or its designee. The Sponsor must approve the destruction of any study drug and receive a copy of the destruction record(s).

#### **8.2.5 Administration of Study Drug**

TOL-3021 or placebo will be administered weekly via an intramuscular injection of 0.5 mL for 52 weeks. Injections will be administered at the study site at Randomization and Weeks 1, 2, and 4 and at week 3 to the first 6 subjects aged 14-<18 years of age in cohort B. During these visits, subjects and any designated caregiver(s) will be given instruction on administration of study drug at home. Study drug injections after Week 4 (and at Week 3) will be administered at home. Subjects will be provided with all necessary supplies for administration of the injections including tuberculin syringes for drawing study drug up from vial, 23 gauge needles in the length(s) appropriate for subject age, weight, and injection site to be used (see Table 4 as a guide), alcohol wipes, gauze pads, band aids, and a sharps container. An exact number of study drug vials to cover injections over the interval to the next visit will be dispensed. Study drug will be packaged for transport at the clinic in an appropriate protective enclosure. Subjects will be instructed to place the study drug in their refrigerator in an area where it will not be disturbed. Thorough hands on training will be provided by trained study staff and will include the following:

- Locating site for injection, including the deltoid muscle in the arm and the vastus lateralis muscle in the thigh. Subjects 18 years or older may also be given the option of using the ventrogluteal site.
- Procedure for drawing study drug into syringe and attaching appropriate needle.
- Preparing the injection site.
- Administering the injection, including how to insert the needle at a 90 degree angle (straight) into the muscle with a rapid, smooth, motion all the way up to the hub of the needle, steadying the syringe, and, using gentle pressure to administer the drug over a 3 to 5 second period, withdrawing the syringe and holding a sterile gauze pad over the injection site to contain any droplets of blood.
- Disposal of the needle and syringe into a sharps container.
- Recording the date and time of the injection in the diary; subjects may also be asked to take a photograph of the injection site using a mobile phone.

Detailed written and diagrammatic instructions will be given to each subject and caregiver(s) so that they are well prepared to administer the study drug at home.

Subjects will be instructed to rotate injection sites so that the same site is not used for consecutive injections, and to avoid using the injection site arm or leg for strenuous activity during the following 24 hours. Subjects will be instructed to contact the study site immediately to report any unusual pain/tenderness, redness, swelling, bruising, burning, itching, or ulceration of subcutaneous abscess at the injection site.

**Table 4. Selection of Needle Length for Study Drug Administration**

Injection Site	Subject Specifics	Needle Length (inches)
Deltoid		3/4- 1
Anterolateral thigh		1
Ventrogluteal		1 – 1 ½
	≥18; >200 lbs; female	1 ½
	≥18; >260 lbs; male	1 ½

